6.1.4 Required training and MSC administration

MSCs will be manufactured at the Case Cancer Comprehensive Center Cellular Therapy Lab at Case Western Reserve University in Cleveland, Ohio with supervised and trained personnel. The MSCs, in the

appropriate dose, will be shipped to the Cell Therapy Laboratory at University Hospital where the MSCs will be thawed and diluted 1:1 with Plasmalyte A and administered within 4 hours of the thawing process. All personnel in the Stem Cell Laboratory are qualified in the processing on MSCs for patient administration. The thawed MSCs will then be administered to the patients in a monitored setting with telemetry and pulse oximetry.

MSC Administration. This is a randomized, double blinded trial and after enrollment, patients will be randomized in a 1:1:1 fashion to receive placebo (Plasmalyte A), 1×10^6 MSC/kg., or 3×10^6 MSC/kg. The rationale for selection of these doses was presented in the Research Strategy. IV MSC infusions will occur in a monitored inpatient room on the Surgical Intensive Care Unit at the Roudebush VA Hospital or the Clinical Research Center at IU Health University Hospital. Patients will be pre-medicated with hydrocortisone (25-50 mg. IV) and diphenhydramine (Benadryl, 25-50 mg. IV). All subjects will be monitored throughout the MSC infusion procedure with vital signs and pulse oximetry beginning 15 minutes prior to infusion and ending 2 hours post procedure. They will also be evaluated for clinical signs of pulmonary distress including progressive or sustained hypoxia, dyspnea, and tachycardia. If enrolled patients develop any of the following conditions within 24 hours of planned infusion, MSC delivery will be halted:

- a. Fever (Temperature increase to $\geq 100.4^\circ\text{F}$)
- b. Upper respiratory tract infection diagnosed by independent health provider.
- c. Significant shortness of breath
- d. Unanticipated change in consciousness or neurological change
- e. Major adverse cardiac event

All patients will be admitted for continued observation to the SICU at the Roudebush VA Hospital or the Clinical Research Center at IU Health University Hospital. The patient will be observed for two hours after the study product infusion and then discharged home. The patient will be re-examined on Days 7 and 14 for treatment related adverse events.

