- MSCs products will be thawed and diluted 1:1 with Plasmalyte. Samples for cell viability (i.e. Trypan Blue and/or 7AAD) and 14-day bacterial sterility testing will be obtained. Viability >70% will need to be entered in the Certificate of Analysis before the product is released for administration.
- In the event of a positive sterility test result after products infusion, the physician and patient will be informed, and the results reported to the IRB and FDA. The positive result will be reported in an information amendment submitted to the IND in a timely manner, preferably within 30 calendar days after initial receipt of the positive culture test result (21 CFR 312.31).
 - Should cultures for detection of bacteria and fungi become positive, the Principal Investigator of the study will be notified. The PI will then notify the patient and the appropriate antibiotics will be started based on sensitivities of the identified organism.
 - A physical examination of will be conducted within 24 hours at which time a complete blood count will be obtained. Should there be an elevate white blood cell count (> 11.5K), the patient will be admitted to the hospital for intravenous antibiotics or antifungal medications. Should there be no clinical evidence of infection the patient will be treated for 7 days with oral antibiotics or anti-fungal medication
 - A systematic review of potential sources of contamination will be conducted with emphasis on skin preparation and draping and the components of the cell transport and preparation system. An examination of the sterile packaging for disposable components and the process of sterilization of non-disposable components will be performed as part of this review.
 - An infection as a result of contamination will be reported as an adverse event within 15 calendar

Table 2. Follow-Up Schedule

Procedures	Baseline	Day 0 MSC (4-6 hr. visit)⁹	Day 7 F/U (+/- 2 days)	Day 14 F/U (+/- 5 days)	Mo 1 F/U (+/- 1wk)	Mo 6 F/U (+/- 2wk)	Mo 12 F/U (+/-2 wk)	Mo 18 F/U (+/-2 wk)	Mo 24 F/U (+/-4 wk)
Informed Consent	X								
Medical History	X								
Physical Exam	X	X	X	X	X	X			
Vital Signs	X	X	X	X	X	X	X	X	X
Con. Medications	X	X	X	X	X	X	X	X	X
AE/SAE Evaluations	X	X	X	X	X	X	X	X	X
QoL Questionnaires	X					X	X	X	X
Infectious Disease Labs ¹	X								
Laboratory Evaluations	X ²				X ³				
12 Lead ECG	X ⁸				X				
Duplex Ultrasound	X					X	X	X	X
Randomization	X								
PET CT	X			X					
CT Angiogram ⁹							X		X
Blood Sample ⁴		X ⁵	X	X	X	X	X	X	X

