Infusion Reaction Assessment ^{6,7}		X		X					

1. Infectious disease testing including basic HIV, Hepatitis C testing. HLA Typing will be performed at baseline, but is not exclusionary to enrollment, nor a protocol deviation if HLA results after study product infusion.
2. Baseline labs ONLY = CBC with differential, Glucose, Sodium, Potassium, Chloride, CO2, BUN, Creatinine, eGFR, hs-CRP, CPK, HbA1C, Total Bilirubin, Total Protein, Albumin, Alkaline phosphatase, alanine transaminase (ALT), aspartate transaminase (AST), platelet count, PT/INR, Pregnancy (childbearing Females-baseline only).
3. Follow-up labs = CBC with differential, Glucose, Sodium, Potassium, Chloride, CO2, BUN, Creatinine, eGFR, hs-CRP, CPK, Albumin, platelet count.
4. Peripheral blood draw for ancillary studies is up to 34 ml.
5. Day of MSC administration blood sample to be collected prior to study product infusion (can be done at physical exam if within 2 hours of infusion).

6. Infusion reaction assessment will include: clinical observation for signs of tachycardia and cutaneous flushing and vital signs (blood pressure, heart rate, respiratory rate, and temperature) at 15 min intervals throughout infusion starting 15 min prior to infusion. Post infusion vital signs will be monitored at 15 min, 30 min, 1 and 2 hours.
7. Oxygen saturation will be continuously monitored throughout infusion by pulse oximetry starting 15 min prior to infusion through 2 hours post infusion.
8. Baseline ECG may be obtained any time prior to study product infusion.
9. CT Angiograms beginning at year 1 and performed annually throughout subjects' participation are considered Standard of Care.

Table 3. Long-Term Follow-Up Schedule

	Mo 30 (+/-4wks)	Mo 36 (+/-4wks)	Mo 42 (+/-4wks)	Mo 48 (+/-4wks)	Mo 54 (+/-4wks)	Mo 60 (+/-4wks)
Duplex Ultrasound ¹	X	X	X	X	X	X
CT Angiogram ³		X		X		X
QOL Questionnaire	X	X	X	X	X	X
AE/SAE Evaluations	X	X	X	X	X	X
Blood Sample ²	X	X	X	X	X	X

1. Duplex ultrasound measured every six months is considered standard of care.

2. Peripheral blood draw for ancillary studies is 34 ml.

3. CT Angiograms performed annually are considered Standard of Care.

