Primary attention in Aim 1 will focus on the detection of cellular immunosuppression activity coincident with MSC administration in both proliferation (six decreasing and one increasing) and function (three decreasing functional outcomes). Ten mixed model repeated measures with a fixed term for MSC dose and their appropriate baseline covariate will be fit. The denominator degrees of freedom will be estimated by the method of Kenward and Rodger.¹² A compound symmetry covariance structure will be fit if the model with the unstructured covariance does not converge. For these data the directionality of superiority or inferiority will be assessed. Specifically, the alternative hypotheses are that (1) three T-cell counts (CD4⁺CD28⁻, CD8⁺CD28⁻ T-cells and Th-17⁺ T-cell) will be decreased; (2) CD28⁻ T-cell function will be inhibited (decreased; as measured by IFN- γ -producing cells, Perforin-producing cells, and CD57 expression); (3) T-regulatory cells (CD4⁺Fox3P⁺ T-regs) will be increased; and (4) monocytes will be decreased (fewer CD45⁺CD14⁺⁺CD16⁻, CD45⁺CD14⁺CD16⁺, CD45⁺CD14dim/CD16⁺⁺). To assess the individual hypotheses, the model-derived, confidence interval for the intercept will be reported. Confidence intervals at the 95% level from the same models will be constructed to estimate the difference, or contrast, between routes of administration

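### The only research blood sample scheduled before infusion may be drawn after hydrocortisone premedication, so the baseline for the ten immune-cell models is not protected

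*Combined protocol and SAP*

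**What the plan says.** **Sampling.** The research blood row of Table 2 (section 7.1), "Blood Sample ⁴", is marked at Day 0, Day 7, Day 14 and Months 1, 6, 12, 18 and 24. Its Baseline column is empty. Footnote 4 gives the purpose: "Peripheral blood draw for ancillary studies is up to 34 ml". Footnote 5 sets the Day 0 timing: "Day of MSC administration blood sample to be collected prior to study product infusion", with the allowance that it "can be done at physical exam if within 2 hours of infusion".

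**Premedication.** Section 6.1.4 states: "Patients will be pre-medicated with hydrocortisone (25-50 mg. IV) and diphenhydramine (Benadryl, 25-50 mg. IV". It is not limited to the MSC arms. No clock time is given, and no order relative to the blood draw.

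**Analysis.** Section 9 states: "Ten mixed model repeated measures with a fixed term for MSC dose and their appropriate baseline covariate will be fit". The baseline sample is not named. For the individual hypotheses, "the model-derived, confidence interval for the intercept will be reported". The Synopsis describes the efficacy endpoints, which it labels exploratory, as changes in circulating inflammatory cell phenotypes; section 3.4 likewise speaks of changes in the immune measures.

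**The concern.** The outcomes are counts and functions of T cells, regulatory T cells and monocytes, and the premedication includes a corticosteroid. The protocol itself treats immunosuppressant use as relevant, since exclusion 10 bars conditions that require it. If hydrocortisone has moved a cell measure by the time of the draw, the baseline carries that shift. Samples from Day 7 onward follow no protocol premedication, so the shift would not cancel in a change from baseline.

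Giving the same premedication to every arm protects the comparison between arms, but not within-arm change. The plan relies partly on the latter: it describes efficacy as change and assesses each hypothesis through an intercept. Nothing requires the draw time and premedication time to be recorded together, so affected baselines could not reliably be identified afterwards.

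**Working it through.** **1. Is Day 0 the only candidate baseline?** The screening panel ("Baseline labs ONLY = CBC with differential", followed by chemistry, hs-CRP and similar) lists no T-cell, regulatory T-cell or monocyte-subset assay. The serum taken before MSC administration in section 7.1 is for antibodies against the cells. That leaves the Day 0 research draw. This is an inference from Table 2, because section 9 does not say it.

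**2. How many models are affected?** Section 9 summarises 6 decreasing + 1 increasing + 3 functional = 10. Its listed hypotheses give 3 T-cell counts + 3 CD28⁻ functions + 1 regulatory T cell + 3 monocyte subsets = 10. The two counts agree, and every model takes a baseline covariate.

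**3. Inputs for size.** From the documents: 12 per arm. Assumed, because the documents give no figure: the steroid shift *d* (in SD), the fraction *f* of Day 0 samples drawn after premedication, and the baseline-to-follow-up correlation *r*. One follow-up visit is considered, with no true effect.

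**4. Within-arm change.** Bias = *f* × *d*. Variance of one change = 2(1 − *r*) + *f*(1 − *f*)*d*². SE = √(variance/12). With *r* = 0.6 and *f* = 0.5:

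| *d* | bias | variance | SE | bias/SE |
|---|---|---|---|---|
| 0.25 | 0.125 | 0.8 + 0.0156 = 0.8156 | 0.261 | 0.48 |
| 0.5 | 0.25 | 0.8 + 0.0625 = 0.8625 | 0.268 | 0.93 |
| 1.0 | 0.50 | 0.8 + 0.25 = 1.05 | 0.296 | 1.69 |

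Rejection rates of a paired t-test (11 df, nominal 5%), from 4,000 simulated trials per scenario:

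| *d* | *f* = 0.25 | *f* = 0.5 | *f* = 1 |
|---|---|---|---|
| 0.25 | 5.1% | 7.6% | 15.1% |
| 0.5 | 7.5% | 13.9% | 40.7% |
| 1.0 | 12.1% | 32.9% | 93.7% |

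With no shift the simulated rate is 4.3%. A noncentral t calculation from the bias/SE values above gives 7.2%, 13.7% and 33.9% at *f* = 0.5, in agreement with the simulation.

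**5. Randomised contrast, draw order unrelated to arm.** Baseline-adjusted comparison of two arms in the same simulation: bias about zero and type I error 4.1% to 5.4%. A mix of draws before and after the steroid adds noise to the covariate. SE ratio = √{[1 − *r*²/(1 + *f*(1 − *f*)*d*²)] / (1 − *r*²)}. At *f* = 0.5:
- *d* = 0.5, *r* = 0.5: √(0.7647/0.75) = 1.01.
- *d* = 1, *r* = 0.7: √(0.608/0.51) = 1.09.
- *d* = 1, *r* = 0.6: √(0.712/0.64) = 1.05. The simulated SE goes from 0.330 to 0.349, a ratio of 1.06.

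**6. Randomised contrast, draw order differing by arm.** With 75% against 25% drawn after premedication and *r* = 0.6, bias = [0.6/(1 + 0.1875*d*²)] × 0.5*d*. This gives 0.14 SD at *d* = 0.5 and 0.25 SD at *d* = 1; simulation gives 0.146 and 0.251, with type I error 6.6% and 10.6%.

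**The case against.** **The sequence is permitted, not shown.** Section 6.1.4 gives no time for the hydrocortisone, and a site that draws first complies fully. This stands, and the point is worded accordingly.

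**The rejection rates belong to a test the plan does not specify.** They are for an unadjusted within-arm change, whereas section 9 specifies mixed models with a baseline covariate. If the response is the follow-up value and baseline is centred on its observed mean, the intercept does not move with a shifted baseline. If baseline is left uncentred, the intercept does move, by about slope × shift, but it is non-zero even with no steroid, so comparing it with zero is uninformative. The bias carries over in full to the intercept when the response is change and the covariate is centred. Section 9 does not say which model is meant. This stands: the rates illustrate what could happen to within-arm change and are not error rates of the planned models.

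**A reader might infer that the steroid would pass for an MSC benefit.** The documents do not support that. Nine of the ten hypotheses are decreases, and a steroid that lowered the baseline would make later values look higher, against those nine. Neither the direction nor the size of the shift is given for any subset.

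**The controlled comparison survives.** Premedication is not arm-specific, a shared shift would also appear under placebo, and no passage suggests that draw order differs by arm. This stands, subject to step 6 of the check. It does not rescue the within-arm descriptions of change, which the plan also intends to report.

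**Conclusion.** The gap is real: a baseline drawn after hydrocortisone complies with the protocol as written, affects the covariate of all ten immune models, and could not reliably be traced later. Its consequence is conditional. Within-arm change, and intercept inference on change, would be biased by about *f* × *d*; the 8% to 33% range rests on an assumed shift of 0.25 to 1 SD, half the samples drawn after, *r* = 0.6 and one follow-up visit. At the smallest assumed shift the inflation is slight.

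Two stronger readings are tempting. One is that the baselines are contaminated; the documents only fail to prevent it. The other is that the randomised dose comparisons are invalid; they remain unbiased unless draw order differs by arm, with the SE rising by about 1% to 9% for shifts of 0.5 to 1 SD, correlations of 0.5 to 0.7 and half drawn after. Nor can later samples be called free of steroids altogether: no later scheduled visit carries protocol premedication, but nothing bars steroid use during follow-up. The endpoints are exploratory, yet correcting the rule costs almost nothing and a lost baseline cannot be recovered, so the change is worth making.

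**What to change.** Replace the timing rule in Table 2, footnote 5, with: *Day 0 research blood sample to be collected before any premedication and before study product infusion.* Record the clock times of the draw and of the premedication on the case report form. In section 9, name this sample as the baseline covariate for the ten immune models.

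If patients have already been treated, establish the order from source records where possible and add a sensitivity analysis excluding baselines drawn after premedication.

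The cost is the order of a blood draw at a visit already scheduled, plus two recorded times. No change to the premedication is proposed.

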7.2 Study Data

Eligible subjects will be invited to participate in the study on a first-come basis. Potential donors must provide informed consent to participate. To be eligible for participation, subjects must be between 40 and 80 years of age with an AAA 30-50 in MTD.

7.2.1 Collection of data

At the discretion of the Investigator and subject to Indiana University School of Medicine requirements, data (**Table 1**) will be collected from each eligible subject providing signed informed consent.

7.3 Procedures for Study Closure

7.3.1 Routine study close-out

The study will end when Indiana University School of Medicine has obtained all data necessary to complete its studies of the test product. Study close-out will follow Indiana University School of Medicine standard procedures and may include, but is not limited to, review of regulatory documents, collection of completed case report forms, reconciliation of study records, removal or destruction of ancillary study supplies, and informing the Investigator of remaining obligations (e.g., record retention, final report submission to the IRB, financial disclosure updates, etc.).

7.3.2 Suspension or premature termination of the study

This study may prematurely terminate at any time because of a regulatory authority decision, a change in opinion of the IRB, or at the discretion of the Investigator or Sponsor. If this trial is temporarily suspended or prematurely discontinued, Indiana University School of Medicine will promptly notify the Investigator(s) and provide instructions. If the study is temporarily suspended, Indiana University School

of Medicine will provide guidance on timing and procedures for resuming the study. If the study is prematurely discontinued, all study materials must be collected and all study forms completed to the extent possible. All such materials must be returned to Indiana University School of Medicine upon request.

8. DATA QUALITY ASSURANCE

The study site will be responsible for the accuracy of data. Indiana University School of Medicine or its agent may periodically conduct monitoring visits to ensure the quality of data collection.

9. STATISTICAL METHODS

The safety of systemic administration of allogeneic MSCs will be measured by treatment-related adverse events. Treatment-related adverse events will be categorized by overlapping systems and severities. The three categories of systems are cardiovascular, respiratory, or infectious. Two categories of severity will be serious adverse (SAE) and major adverse cardiac events (MACE). For completeness, instances of adverse events may appear in more than one category. Within each of these categories adverse events will be listed in descending order of frequency for the treatment-group. In addition, for each category, the sum and difference between the two routes of delivery of the proportions will be reported as percent incidence. Confidence Intervals at the 95% confidence level and *P*-values for these four groups will be calculated. Since four previous trials have not reported adverse events with MSC treatment, confidence intervals will be generated by the method of the Wilson Score Interval because they are robust, with good coverage probability even for small number of trials and are not degenerate near zero. These intervals will be used to summarize the data rather than as any formal inferential statement. No adjustment for multiplicity will be made.

Primary attention in Aim 1 will focus on the detection of cellular immunosuppression activity coincident with MSC administration in both proliferation (six decreasing and one increasing) and function (three decreasing functional outcomes). Ten mixed model repeated measures with a fixed term for MSC dose and their appropriate baseline covariate will be fit. The denominator degrees of freedom will be estimated by the method of Kenward and Rodger.¹² A compound symmetry covariance structure will be fit if the model with the unstructured covariance does not converge. For these data the directionality of superiority or inferiority will be assessed. Specifically, the alternative hypotheses are that (1) three T-cell counts (CD4⁺CD28⁻, CD8⁺CD28⁻ T-cells and Th-17⁺ T-cell) will be decreased; (2) CD28⁻ T-cell function will be inhibited (decreased; as measured by IFN- γ -producing cells, Perforin-producing cells, and CD57 expression); (3) T-regulatory cells (CD4⁺Fox3P⁺ T-regs) will be increased; and (4) monocytes will be decreased (fewer CD45⁺CD14⁺⁺CD16⁻, CD45⁺CD14⁺CD16⁺, CD45⁺CD14dim/CD16⁺⁺). To assess the individual hypotheses, the model-derived, confidence interval for the intercept will be reported. Confidence intervals at the 95% level from the same models will be constructed to estimate the difference, or contrast, between routes of administration

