By my signature below, I agree to conduct this Study in accordance with the Clinical Trial Protocol, current Good Clinical Practice (cGCP) and Good Laboratory Practice (cGLP) guidelines, obligations as set forth in Title 21 CFR Parts 812, 54, 5,6 and 11 (as applicable), and any applicable regulatory laws. I will make no changes to protocol-defined procedures without written permission from the Sponsor.

I understand that Investigational Use Products may be used **only** for the purposes explicitly described in this protocol.

I further agree to treat the results of this Study as confidential information and will not submit the results of the Study for publication without prior written authorization from the Sponsor.

[name]

PRINTED NAME

SIGNATURE

7/15/2021

DATE

SYNOPSIS

Title of Study	Phase I study to examine the safety and efficacy of allogeneic MSCs in suppressing inflammation in patients with small abdominal aortic aneurysm (AAA)
Objectives	Assess the safety and efficacy of systemic (IV) administration of escalating doses of allogeneic MSCs in modulating immune cell phenotypes and suppressing aortic inflammation in patients with small AAA.
Planned Number of Subjects and Duration of Involvement	36 patients
Patient Population	Abdominal aortic aneurysms (AAA) patients
Investigational Product Name	Allogeneic mesenchymal stem cells
Methodology Overview	In a double blind, Phase I trial, 36 patients with AAA measuring 30-50mm in maximal transverse diameter (MTD) will be randomized in a 1:1:1 fashion to receive either 1.0×10^6 MSCs/kg (n=12), 3.0×10^6 MSCs/kg. (n=12), or placebo (Plasmalyte A) (n=12) delivered intravenously. The primary safety endpoints will be incidence of treatment related adverse events at 24 months post MSC-administration. Exploratory primary efficacy endpoints will be changes in circulating inflammatory cell phenotypes and aortic inflammation as measured by CT. The treatment period will involve long-term follow-up through 5 years. The incidence of surgical intervention, aneurysm related death, quality of life, and major adverse cardiac events will be recorded.

Table 1 Abbreviations

AAA	Abdominal Aortic Aneurysm
AE	Adverse Event
AMI	Acute Myocardial Infarction
ASC	Adipose derived MSC
bMSC	Bone marrow derived MSC
CTSI	Clinical and Translational Sciences Institute
DSMB	Data Safety Monitoring Board
eGFR	Effective Glomerular Filtration Rate
GVHD	Graft Versus Host Disease
IFN- γ	Interferon- γ ,
IL	Interleukin

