3.3 Proposed Intended Use Statement

Allogeneic MSCs are a novel therapeutic option to suppress growth of small AAA. Human MSCs are intended for investigational use only by selected investigators familiar with their use and experienced in conducting clinical studies. Human MSCs may only be administered to human subjects participating in clinical studies sponsored/approved by Indiana University School of Medicine, and who have provided formal written consent.

3.4 Study Objectives.

The principal objective of this study is as follows:

Assess the safety and efficacy of administration of allogeneic MSCs in patients with small AAA.

This study will test the hypothesis that administration of MSCs in doses of 1×10^6 MSCs/kg. and 3×10^6 MSCs/kg demonstrate safety in patients with small AAA. This trial will also test the hypothesis that MSCs, in a dose dependent fashion (1×10^6 MSC/kg. vs. 3.0×10^6 MSC/kg.), promote the frequency and immune suppressor function of Treg cells and decrease AAA inflammation as measured by computed tomography. In an double blinded, Phase I trial, 36 patients with AAA measuring 35-50 mm in maximal transverse diameter (MTD) will be randomized in a 1:1:1 fashion to receive intra-venously either a single dose of 1×10^6 MSCs/kg., 3×10^6 MSCs/kg. , or placebo (Plasmalyte A) (n =12/group). The primary safety endpoints will be incidence of treatment related adverse events accrued over 24 months. Efficacy measures are changes in frequency and immune suppressor function of Tregs, number and cytotoxic activity of CD4+/CD8+ CD28- T-cells, activated monocytes, and changes in aortic inflammation as measured by PET CT compared to baseline. Secondary endpoints measured out to year 5 will include changes in IL-10 and Tr1 levels. Duplex ultrasound measurements of the AAA, which is considered standard of care, will be recorded as change in aortic inflammation during long-term follow-up. Incidence of surgical intervention, aneurysm related death, quality of life, and major adverse cardiac events will be recorded through year five (5).

Completion of this study will determine if MSCs are safe in patients with AAA and provide critical insights that will direct a placebo-controlled, Phase II randomized trial.

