11. RISK ANALYSIS

11.1 Potential Risks of the Investigational Product and Clinical Investigation

Study sites will not be provided with an investigational device.

The types of risk associated with injection of allogeneic MSCs align with those associated with injection of autologous bone marrow mononuclear cells (ABMNCs), most notably rash, mild fever, and myalgia. These risks are mild and rare. These risks are all stated in the consent form.

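### Safety is specified only on treatment-related events: no all-cause SAE or MACE summary by randomised arm is planned, and no placebo contrast is named

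*Combined protocol and SAP*

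**What the plan says.** The endpoint definition is consistent across three places.

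- Synopsis: "The primary safety endpoints will be incidence of treatment related adverse events at 24 months post MSC-administration".
- Section 3.4: "The primary safety endpoints will be incidence of treatment related adverse events accrued over 24 months".
- Section 9: "The safety of systemic administration of allogeneic MSCs will be measured by treatment-related adverse events", followed by "Treatment-related adverse events will be categorized by overlapping systems and severities". The categories are three body systems (cardiovascular, respiratory, infectious) and two labelled as severity (SAE and MACE).

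For the between-group comparison, section 9 says that, in each category, "the sum and difference between the two routes of delivery of the proportions will be reported as percent incidence". It then refers to four groups. The trial has one route (intravenous) and three arms of 12. Intervals are 95% Wilson score intervals, and their status is stated: "These intervals will be used to summarize the data rather than as any formal inferential statement".

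Other sections bear on the same events:

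- Section 10.1 has all SAEs reported to the sponsor and defines MACE (including death, MI, stroke, TIA, heart failure admission and aneurysm rupture). Neither carries a relatedness condition. It gives a 6-month collection period for MACE, and says non-serious adverse events will be neither collected nor analysed by the sponsor.
- The synopsis and section 3.4 say MACE, surgery and aneurysm-related death will be recorded, over follow-up to year 5. No analysis is attached.
- Section 4.2 leaves the PI unblinded; co-investigators, coordinators and patients are blinded.
- Section 9.2 promises summary analyses of safety profiles without further detail.

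**The concern.** The trial has a concurrent randomised placebo arm. A comparison of all events by arm estimates the effect of the infusion without anyone having to decide what caused an individual event. Counting only related events puts a judgement between the data and the result.

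That judgement is hardest for the events that matter most here. In patients aged 40 to 85 with an aneurysm, MI, stroke, heart failure admission and death occur anyway, and follow-up for the endpoint runs 24 months after a single infusion. If MSCs made such events more frequent, each extra event would look like the background ones. The planned tables would show the excess only to the extent that events were attributed to the infusion. If attribution differed between arms, which is possible with an unblinded PI, the tables could also show a difference that is not there or reverse one that is.

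**Working it through.** **What the plan's figures allow.** The documents give no event rate, effect size, power or attribution share for safety. The only figure to reproduce is the sample size: 3 × 12 = 36, which agrees. Everything below is illustration under stated assumptions.

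**Assumptions.** 24-month risk of at least one SAE is 55% on MSC (both doses together, n = 24) and 30% on placebo (n = 12), a true difference of 25 points. A share f of events is judged related.

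**Equal f in both arms, at most one event per patient.** Related-event difference = f × (0.55 − 0.30). Chance of no related event in 24 MSC patients = (1 − 0.55f)^24.

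**Equal f, Poisson counts per patient.** Event means that give the same risks are −ln(0.45) = 0.799 and −ln(0.70) = 0.357. Related-event risk = 1 − exp(−f × mean). Chance of no related event in 24 MSC patients = exp(−24 × f × 0.799).

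| f | Difference, one event | Difference, Poisson | P(no related event in 24), one event | Same, Poisson |
|---|---|---|---|---|
| 10% | 2.5 points | 7.7% − 3.5% = 4.2 points | 25.7% | 14.7% |
| 25% | 6.3 points | 18.1% − 8.5% = 9.6 points | 2.9% | 0.8% |
| 50% | 12.5 points | 32.9% − 16.3% = 16.6 points | 0.04% | 0.01% |

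For comparison, 24 × 0.55 = 13.2 MSC patients would be expected to have at least one SAE of any cause.

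**Limit f = 0.** The tables read 0/24 (Wilson 95% interval 0 to 13.8%) and 0/12 (0 to 24.2%) whatever the true excess.

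**Unequal f (one event per patient).**
- f = 5% on MSC and 20% on placebo: 0.05 × 55% − 0.20 × 30% = 2.75% − 6.0% = −3.25 points. The true +25 points has changed sign.
- No true effect (30% in both), f = 20% on MSC and 5% on placebo: 6.0% − 1.5% = +4.5 points. A difference has appeared from nothing.

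**What the all-cause comparison could show.** Exact power of Fisher's test, two-sided 5%, at 55% against 30%: 23% for 24 against 12 and 14% for 12 against 12. As an example table, 10/24 against 2/12 gives a difference of 41.7% − 16.7% = +25 points, Newcombe 95% interval −8.0 to 47.9, Fisher P = 0.26.

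**The case against.** The strongest reply is that the all-cause information is not lost. SAEs are reported and MACE is defined without a relatedness condition, MACE is a listed outcome to year 5, and section 9.2 leaves room for a general safety summary. This stands. A reader might infer that the all-cause comparison will never be made; the documents support only that it is not specified. Section 9 also drops the words treatment-related after its opening sentences, so reading its SAE and MACE categories as related events is an inference. It is the natural one, because the categories are introduced as a breakdown of that set.

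A reader might also infer from section 11.1, which describes the risks as "most notably rash, mild fever, and myalgia", that assessors are primed to call a late MI unrelated. The documents do not show this. The wording is not exclusive, section 6.1.4 directs attention to pulmonary distress, and the remark about four previous trials serves to justify the Wilson interval. Nor can it be said that no causality criteria or assessor exist: none appear in the text available, but a page between sections 10.1 and 11 was removed from it.

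The relatedness filter is not universal. The stopping rules for rupture and for expansion count events in the MSC group without it, though with no placebo comparison; the death rule does require relatedness.

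Relatedness is also not the only gap. Because of the routes-of-delivery wording, section 9 names no placebo contrast even for related events, so deleting treatment-related would not by itself create one.

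**Conclusion.** The point holds as a gap in specification that should be closed. The primary safety endpoint and the section 9 tables are defined on treatment-related events, no all-cause SAE or MACE summary by randomised arm is specified, and the one contrast named does not exist in this trial. Followed as written, the safety result depends on attribution.

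Two stronger readings are not supported. The first is that the filter must bias toward no effect: that follows only if attribution is equal across arms, and with an unblinded PI the distortion could go either way. The second is that an all-cause table would reliably detect harm: in the illustration its power is 23% at best. Its value is an estimate with an interval that does not depend on attribution, which matches the descriptive status section 9 already gives its intervals.

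The size cannot be fixed from the documents. The shrinkage from 25 points to between 2.5 and 4.2 points rests on assumed risks of 55% and 30%, an assumed 10% attribution share equal in both arms, and either one event per patient or Poisson counts.

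**What to change.** 1. In the synopsis, section 3.4 and section 9, add all-cause SAEs and all-cause MACE from infusion to Month 24 as safety measures, each counted as patients with at least one event.
2. In section 9, tabulate them for placebo, 1 million/kg and 3 million/kg, with the planned Wilson interval per arm and a 95% interval (for example Newcombe's) for each dose-minus-placebo difference. Replace the routes-of-delivery and four-groups wording.
3. Keep the treatment-related tables as a supporting display.
4. Reconcile the MACE collection period: 6 months in section 10.1, year 5 in the synopsis and section 3.4. An all-cause MACE table to Month 24 cannot be defined until this is settled.
5. Leave all-cause non-serious adverse events out of this change unless the section 10.1 rule that they are not collected is also changed.

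**Cost.** Text changes in the synopsis and sections 3.4, 9 and 10.1, and one further set of tables. No new type of data is needed for SAEs or MACE, and AE/SAE evaluation is already scheduled at every visit in Tables 2 and 3. The downside is that displayed incidences will include background events, and the dose-minus-placebo intervals will be wide.
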